Participants will be randomised 1:1. Populations will be stratified based on HBsAg level (HBsAg ≤ 3 log IU/mL and > 3 log IU/mL) and whether participants are HBeAg positive or negative. Lower HBsAg has been associated with increased likelihood of HBsAg loss in patients treated with PegIFN-containing regimens [Ren, 2019; Lee, 2018; Yeo, 2019]. With existing therapies different responses have also been observed in HBeAg positive and negative patient populations [Ren, 2019].

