4.2. Primary Endpoint Analyses

HBsAg and HBV DNA assessments from the end of treatment analysis window (Week 48 or Week 36 for Arm 1 and Arm 2 respectively) to the off-treatment Week 24 analysis window will be used to analyse the primary endpoint for each arm. The primary analysis for the primary endpoint will be conducted once the database lock has been achieved and the last participant has completed the Week 72 visit.

The primary efficacy endpoint is achieving a sustained virologic response for 24 weeks after the planned end of GSK3228836 and PegIFN sequential treatment in the absence of rescue medication. Sustained virologic response (SVR) is defined as observing HBsAg <LLOQ and HBV DNA <LLOQ at each analysis window in the 24 weeks after the end of sequential treatment. Analysis windows for the post GSK3228836 treatment assessments are defined in Section 4.2.2.1.

An estimation approach with no hypothesis testing will be used to address the primary objective. The primary assessments of interest are the point estimate of SVR rate and 95% credible intervals. In addition, posterior probabilities that the true SVR rate in each treatment arm is greater than a range of clinically meaningful response rates will be provided. The point estimates for SVR will be calculated using a Bayesian probability approach. Comparisons between treatment arms as defined in the key secondary/exploratory objectives will be assessed using probability inference approaches.

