4.2.1. Definition of Estimands

The primary estimand supporting the primary objective is defined as:

- **Population:** Participants with CHB on stable NA therapy.
- **Treatment:** 300 mg GSK3228836 for 12 or 24 weeks followed by up to 24 weeks of PegIFN therapy while on stable NA therapy.
- **Variable (Categorical):** Participants achieving sustained virologic response (SVR) (HBsAg <LLOQ and HBV DNA <LLOQ) for 24 weeks after the planned end of sequential treatment, without the use of rescue medication.
- **Intercurrent Events:**
 - For discontinuation of, interruption in, or non-adherence to GSK3228836 or PegIFN unrelated to any wide disruptive events (such as COVID-19 pandemic), the data will be analysed as collected (treatment policy strategy).
 - For participants that are ineligible to receive PegIFN, the data will be analysed as collected (treatment policy strategy).
 - Use of rescue medication will be incorporated in the definition of the endpoint (composite strategy).
 - For wide disruptive events (such as COVID-19 pandemic) leading to discontinuation of, significant interruption in, or non-adherence to GSK3228836 and PegIFN, data collected after the intercurrent event will

be set to missing and the response will be imputed assuming missing at random in the Bayesian model. Additional details provided in Section 4.2.2.2 (hypothetical strategy).

- **Population Summary:** The percentage of participants in each treatment group who achieve sustained virologic response (SVR) (HBsAg <LLOQ and HBV DNA <LLOQ) for 24 weeks after the planned end of sequential treatment without rescue medication usage.

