$$P(p_1|data) = P\left(\frac{e^{\theta_1}}{1 + e^{\theta_1}} | data\right)$$

$$P(p_2|data) = P\left(\frac{e^{\theta_2}}{1 + e^{\theta_2}} | data\right)$$

$$P(p_3|data) = P\left(\frac{e^{\theta_3}}{1 + e^{\theta_3}} | data\right)$$

$$P(p_4|data) = P\left(\frac{e^{\theta_4}}{1 + e^{\theta_4}} | data\right)$$

The posterior distribution of the arm-level SVR rate will be derived using a mixture of the posterior distributions of SVR rate for each analysis stratum in that arm. The weights are proportional to the sample size of each analysis stratum in each arm:

$$P(p|data) = \sum_{g=1}^4 w_g P(p_g|data), \text{ where } w_g = \frac{n_g}{\sum_{g=1}^4 n_g}$$

Posterior probabilities of SVR rates exceeding a range of clinically meaningful response rates, e.g., 30%, 35%, 40%, will be generated using the approach specified above for each arm. If monotherapy in study 209668 (B-Clear) is deemed successful, then posterior probabilities will be derived for a difference > 10% and <15% of the SVR rates between any B-Together arm and the B-Clear chosen arm to evaluate whether sequential therapy is successful.

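### SAP 4.2.2 defines the arm-level SVR posterior as a mixture of stratum posteriors, not the posterior of the weighted-average rate; if followed, the primary credible interval is too wide and the threshold probabilities are distorted

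*SAP*

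**What the plan says.** SAP 4.2.2 fits one Bayesian logistic model to both arms and obtains a posterior for the SVR rate p_g in each of four strata (HBsAg level by HBeAg status). It then moves to arm level: "The posterior distribution of the arm-level SVR rate will be derived using a mixture of the posterior distributions of SVR rate" across those strata. "The weights are proportional to the sample size of each analysis stratum in each arm". The formula agrees with the words: P(p|data) = Σ w_g P(p_g|data), with w_g = n_g / Σ n_g.

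The threshold outputs use the same construction: "Posterior probabilities of SVR rates exceeding a range of clinically meaningful response rates, e.g., 30%, 35%, 40%, will be generated" by that approach for each arm. So would a conditional contrast with the monotherapy study: "If monotherapy in study 209668 (B-Clear) is deemed successful, then posterior probabilities will be derived for a difference" between arms of the two studies.

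SAP 4.2 makes these the headline results: "The primary assessments of interest are the point estimate of SVR rate and 95% credible intervals", with threshold probabilities in addition. SAP 4.2.1 sets the population summary as one percentage of responders per arm.

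Protocol 4.1 explains why strata were used. "Lower HBsAg has been associated with increased likelihood of HBsAg loss in patients treated with PegIFN-containing regimens", and "With existing therapies different responses have also been observed in HBeAg positive and negative patient populations".

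**The concern.** A percentage of responders in an arm is p_arm = Σ w_g p_g, so its posterior comes from averaging the four rates within each draw. A mixture of the four posteriors answers a different question: what is the rate in a stratum drawn at random with probability w_g? Its spread includes the differences between strata, which are not uncertainty about the arm's rate and do not disappear as data accumulate. The protocol's own reasons for stratifying predict that such differences exist.

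At stake are the primary credible interval and the threshold probabilities in each arm, and the B-Clear contrast if it is triggered. The effect on the Arm 1 versus Arm 2 comparison in SAP 4.3.1.3 depends on how the draws of the two arms are paired, which the SAP does not state. Three things are not affected: the stratum-level posteriors, the planned interim in SAP 4.7.3.1 (an unstratified Beta-Binomial), and Table 12 (unstratified by its own statement).

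**Working it through.** **The plan's own precision.** With a Beta(0.5, 0.5) prior, 17 responders of 50 give Beta(17.5, 33.5). Its equal-tailed 95% interval is 22.1%-47.7%, matching the 22%-48% in SAP Table 11, and P(>30%) = 0.735. With 16 responders P(>30%) is 0.628, so 17 is the minimum for the 65% criterion, as Table 12 says. All rows of Table 11 and all minimum counts in Table 12 reproduce.

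**Algebra, with no assumed data.** Let m_g be the posterior mean of p_g and m = Σ w_g m_g.

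- Both versions have mean m.
- Var(mixture) = Σ w_g Var(p_g) + Σ w_g (m_g − m)².
- Var(Σ w_g p_g) ≤ Σ w_g Var(p_g).

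So the mixture variance is never the smaller one. Under the mixture, P(p > t) is Σ w_g P(p_g > t), the average of the stratum-level probabilities.

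**A hand check of the second term.** Take strata of 15/20/5/10 with 9, 5, 2 and 1 responders (17/50). Observed rates are 0.60, 0.25, 0.40 and 0.10, with weights 0.3, 0.4, 0.1 and 0.2. Using observed rates in place of m_g, the between-stratum term is 0.3×0.26² + 0.4×0.09² + 0.1×0.06² + 0.2×0.24² = 0.0354. The whole variance of Beta(17.5, 33.5) is 17.5×33.5 / (51²×52) = 0.0043. The between-stratum term alone is about eight times that.

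**Model fit.** The SAP 4.2.2 model was fitted by MCMC with two chains, 5,000 burn-in and 60,000 kept draws each; R-hat was 1.00 throughout. Normal(0, 10^6) was read as a variance. The SAP gives no prior for the arm coefficient γ_3 and leaves it out of θ_1 to θ_4. The same prior was assumed for it, and it was carried into the arm-specific stratum rates. The average was formed as Σ w_g p_g within each draw. The mixture was formed by drawing one stratum per draw with probability w_g.

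Results at 17/50, over three assumed splits (15/20/5/10, 10/25/3/12, 20/20/5/5). Spread is the weighted SD of the observed stratum rates. The average gave a 95% interval of 22-23% to 46-48% in all nine cases, P(>30%) of 0.72-0.74 and P(>40%) of 0.16-0.18.

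| Spread between strata | Mixture 95% interval | Width relative to average | Mixture P(>30%) | Mixture P(>40%) |
|---|---|---|---|---|
| 0.03-0.05 (near-equal) | 16-17% to 54-55% | 1.4-1.5 | 0.64-0.66 | 0.25-0.26 |
| 0.09-0.10 | 9-13% to 58-63% | 1.9-2.0 | 0.57-0.62 | 0.28-0.33 |
| 0.17-0.19 (wide) | 4-5% to 67-75% | 2.6-3.0 | 0.46-0.58 | 0.34-0.39 |

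P(>35%), close to the observed 34%, was 0.42-0.43 for the average and 0.39-0.47 for the mixture, with no fixed direction.

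**Further cases, average against mixture.**

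- 15/50 with identical 30% rates (strata 20/10/10/10): 19-43% against 14-49%. The excess is present even without observed differences.
- 12/50 (6, 4, 1, 1 of 12/23/5/10): 14-36% against 3-63%; P(>20%) 0.76 against 0.48. Table 12 says 12 responders meet the 65% criterion for 20%; the mixture would miss it.
- 170/500, observed stratum rates 10% to 60%: 30-38% against 9-65%. Ten times the data barely narrows the mixture.

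**Arm comparison, 17/50 against 10/50, split 15/20/5/10.**

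| Output | Spread | Average | Mixture, same stratum label in both arms | Mixture, independent labels |
|---|---|---|---|---|
| Pr(Arm 1 − Arm 2 > 0) | near-equal | 0.94 | 0.94 | 0.88 |
| Pr(Arm 1 − Arm 2 > 0) | wide | 0.96 | 0.96 | 0.73 |
| Pr(Arm 2 − Arm 1 > −0.05) | near-equal | 0.16 | 0.16 | about 0.22 |
| Pr(Arm 2 − Arm 1 > −0.05) | wide | 0.14 | 0.20 | 0.35 |

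**The case against.** The strongest reply is that this is loose notation. The SAP uses P(·|data) as shorthand for the posterior of a quantity. In 4.3.1.3 it speaks of differencing two posterior distributions, which can only mean arithmetic on draws. On that usage, the weighted sum could mean a weighted average of draws. This may be what the program does, and no wrong implementation is shown. But the SAP also uses the word mixture, the formula is the standard form of one, and no section says that rates are averaged within draws. A programmer or independent replicator following the text would build the mixture.

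A second reply is that the figures repair one formula (γ_3 added, with an assumed prior) and read the next one strictly. That is true, but both summaries come from the same draws, so the repair does not create the gap.

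Third, the study is descriptive, the decision framework sits in the iDRC charter, and SAP 4.2.2 attaches no cut-off to its thresholds. So the documents cannot show that any decision would change. This stands, but the primary interval is itself the result to be reported.

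Two technical limits also stand. The variance inequality does not by itself order equal-tailed 95% intervals; the mixture interval was wider in every case computed. And the two versions share only the posterior mean. SAP 4.2.2 does not say whether the point estimate is a mean or a median. In the 9, 5, 2, 1 case the median is about 34% for the average and 28% for the mixture.

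**Conclusion.** The concern holds. As written, the arm-level rule does not estimate the stated estimand, and it bears directly on the primary interval and threshold probabilities. It must be fixed before the final analysis. Across the assumed cases the interval was 1.4 to about 3 times as wide as it should be. Threshold probabilities were too low for thresholds well below the arm's rate, too high for thresholds well above it, and moved either way close to it. The direction of the variance needs no assumed data. The size rests on assumed stratum sizes and responder counts, on the assumed γ_3 prior, and on the text being followed literally. No figure can be given for the B-Clear contrast, because the documents state no B-Clear response rate.

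**What to change.** Replace the mixture sentence and formula in SAP 4.2.2 with this rule: in each MCMC draw, compute p_arm = Σ w_g p_g from that arm's stratum rates and weights, then take the point estimate, 95% credible interval and threshold probabilities from those draws. Say whether the point estimate is the posterior mean or median. State in 4.3.1.3 that arm differences are taken draw by draw from the joint posterior, and that the B-Clear contrast, if triggered, uses the same p_arm draws. If the program already averages within draws, correct only the text and formula to match.

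The cost is one formula, a few sentences and at most one line of code. No new data are needed.

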4.1.1. General Methodology

Participants who prematurely withdrew from study will not be replaced.

In the case of incorrect randomization stratification assignment at the time of randomization, the analyses will be performed based on the actual stratum per data collected in the baseline lab electronic Case Report Form (eCRF). In the case of randomization to the incorrect strata (i.e., if a HBsAg subject is randomised to the HBeAg strata, or vice versa), analysis will be performed based on the actual strata the subject should have been assigned to.

Unless otherwise specified, continuous data will be summarized using descriptive statistics: n, mean, standard deviation (std), median, minimum, and maximum. Categorical data will be summarized as the number and percentage of participants in each category.

Unless otherwise specified, CIs will use 95% confidence levels.

HBV DNA, HBsAg and HBeAg levels below the LLOQ will be imputed for summaries of actual values and change from baseline. The numeric values for HBV DNA <LLOQ (LLOQ=20 IU/mL) will be imputed as 19.9. The numeric values for HBsAg <LLOQ (LLOQ=0.05 IU/mL) will be imputed as 0.04. The numeric values for HBeAg <LLOQ (LLOQ=0.06 U/mL) will be imputed as 0.05.”

HBV DNA (IU/mL) and HBV RNA (copies/mL) levels that are “TND” will be imputed as 1. HBcrAg (Log₁₀ U/mL) values that are “TND” will be imputed as 0. Values <LLOQ are imputed based on the number of significant digits, similar to other lab parameters.

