4.2.2. Main Analytical Approach

A Bayesian model will be fitted using Markov Chain Monte Carlo (MCMC) methods, and will be used to estimate the posterior probability of SVR sustained virologic response for each arm incorporating the baseline analysis stratification factors (Table 1) [Jones, 2011].

The model below differs from the Bayesian hierarchical model specified in the 209348 Protocol Amendment v.1.0 (24-Sep-2021). This hierarchical model included a random effect ψ_g for each strata, an interaction term for treatment by stratum, and was applied separately for each arm. However, when the model was run on data from the administrative interim analyses (AIAs) (see Section 4.7), there were stratum with zero counts which caused perfect prediction of the response variable for some values of the predictors (quasi-complete separation). To address this issue, the hierarchical model was simplified to the Bayesian logistic regression model below, with only fixed effects and combined data across arms.

The number of responders is assumed to follow a binomial distribution:

$$\text{Number of responders } r_g \sim \text{Binomial}(n_g, p_g), \quad g = 1, 2, 3, 4$$

where we define r_g as the number of SVR responders among n_g participants, p_g as SVR rate $\frac{r_g}{n_g}$, and index g refers to the stratum number as defined in Table 1 below.

The analysis model is defined as:

$$\theta_g = \text{logit}(P_g) = \log\left(\frac{P_g}{1-P_g}\right) = \tau + \gamma_1 I_{\{B1+\}} + \gamma_2 I_{\{B2+\}} + \gamma_3 I_{\{\text{Arm}\}}$$

where τ, γ_1, γ_2 , are all parameters. Thus,

$$\theta_1 = \tau$$

$$\theta_2 = \tau + \gamma_1$$

$$\theta_3 = \tau + \gamma_2$$

$$\theta_4 = \tau + \gamma_1 + \gamma_2$$

Priors:

$$\tau \sim \text{Normal}(0, 10^6)$$

$$\gamma_k \sim \text{Normal}(0, 10^6), k = 1, 2$$

Table 1 Baseline Analysis Strata

Stratum	B ₁ : HBsAg	B ₂ : HBeAg
1: HBsAg ≤3 log IU/mL and Negative HBeAg	B ₁ (≤3 log IU/mL)	B ₂ (Negative)
2: HBsAg >3 log IU/mL and Negative HBeAg	B ₁₊ (>3 log IU/mL)	B ₂ (Negative)
3: HBsAg ≤3 log IU/mL and Positive HBeAg	B ₁ (≤3 log IU/mL)	B ₂₊ (Positive)
4: HBsAg >3 log IU/mL and Positive HBeAg	B ₁₊ (>3 log IU/mL)	B ₂₊ (Positive)

The point estimates and 95% credible intervals of sustained virologic response rate in each of the treatment arms will be calculated.

For each arm, the posterior distribution of SVR rate $P(p_g|data)$, $g=1,2,3,4$ will be derived for each analysis stratum using the model specified above:

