 - For wide disruptive events (such as COVID-19 pandemic) leading to discontinuation of, significant interruption in, or non-adherence to GSK3228836 or PegIFN, data collected after the intercurrent event will be set to missing and the response will be imputed using all available data for participants for whom SVR can be assessed. (hypothetical strategy).

Population Summary: Difference in percentage of participants who achieve SVR for 24 weeks after the planned end of sequential treatment between treatment arms

Categorical Variables

The following categorical variables are defined for this objective:

- Achieving SVR (HBsAg <LLOQ and HBV DNA <LLOQ) at the planned end of sequential treatment and over the 24 weeks follow-up for each treatment arm.

Main Analytical Approach

The secondary efficacy comparison of interest is the difference in sustained virologic response rate for 24 weeks after the planned end of sequential treatment between treatment arms:

- Arm 1 vs. Arm 2 in percentage of participants achieving SVR for 24 weeks after the planned end of sequential treatment, without use of any rescue medication.

Comparison between treatment arms will be made by calculating the difference between the posterior distributions of the response rate in each arm which will be summarised to obtain posterior means and CIs. Samples from the posterior distribution of the response rates in each arm will also be used to obtain posterior probabilities of interest. The point estimates of differences in SVR rate with 95% credible intervals will be calculated for the treatment comparisons described in the estimands. Posterior probabilities $\Pr(\text{Arm 1} - \text{Arm 2} > 0)$ and $\Pr(\text{Arm 2} - \text{Arm 1} > -0.05)$ will be presented to aid selection of treatment regimen.

Model Checking and Diagnostics – MCMC Mixing Diagnosis

The same approach in model checking and diagnostics will be applied as for the primary analysis (Section 4.2.2.3).

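### The Arm 1 minus Arm 2 SVR difference uses each arm's own stratum weights, so it falls back to the crude difference and loses the HBsAg/HBeAg adjustment; the effect is small and unbiased, and cheap to remove

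*SAP*

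**What the plan says.** Protocol section 4.1 sets the allocation ("Participants will be randomised 1:1") and the stratification ("Populations will be stratified based on HBsAg level", together with HBeAg status). SAP section 4.2.2 uses the same two factors in a Bayesian logistic model "with only fixed effects and combined data across arms", with an arm indicator in the linear predictor and very diffuse normal priors.

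The model gives a rate for each of four strata. To reach an arm-level rate the SAP averages them: "The weights are proportional to the sample size of each analysis stratum in each arm". For the regimen comparison, SAP section 4.3.1.3 states: "Comparison between treatment arms will be made by calculating the difference between the posterior distributions of the response rate in each arm". The target is the "Difference in percentage of participants who achieve SVR for 24 weeks after the planned end of sequential treatment between treatment arms". The two posterior probabilities from this comparison "will be presented to aid selection of treatment regimen". No common set of weights is given for the contrast.

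Where a participant was stratified incorrectly at randomisation, SAP section 4.1.1 says "the analyses will be performed based on the actual stratum per data collected in the baseline lab electronic Case Report Form (eCRF").

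**The concern.** A model that adjusts for HBsAg and HBeAg should give a regimen comparison that does not depend on which arm happened to receive more low-HBsAg participants. If each arm's rates are averaged over that arm's own stratum mix, any difference in mix goes back into the contrast after the model has allowed for it.

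Both posterior probabilities in SAP section 4.3.1.3 are affected, one of them set against a 5-point margin. The SAP gives informing the Phase III regimen as an aim of the study (section 2), and Protocol section 4.1 describes lower HBsAg as associated with HBsAg loss, so the factors are expected to be prognostic.

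**Working it through.** **The plan's own figures.** Neither document gives operating characteristics for the arm difference. The single-arm figures in SAP section 5 reproduce. With a Beta(0.5, 0.5) prior and n = 50, the minimum responder counts are 12, 17 and 22. P(at least 12 | true rate 30%) = 86.1% (stated 86%), and P(at least 17 | true rate 40%) = 84.4% (stated 84%).

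**Why own-arm weights return the crude difference.** Let arm a have n_ag participants in stratum g, n_a in total and y_a responders, and let p_ag be the fitted rates. With an intercept and an arm term, the likelihood equations force fitted responders to equal observed responders within each arm:

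sum over g of n_ag p_ag = y_a, so sum over g of (n_ag / n_a) p_ag = y_a / n_a.

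The left side of the second equation is the SAP's arm-level rate. The fitted difference is therefore y_1/n_1 - y_2/n_2. This is exact at the maximum-likelihood fit for participants whose SVR status is known, and near-exact for the posterior mean under Normal(0, 10^6) priors. The SAP states no such prior for the arm coefficient; the same one was assumed.

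The difference also splits exactly into two parts:

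sum of mean(w_1g, w_2g) x (p_1g - p_2g) + sum of (w_1g - w_2g) x mean(p_1g, p_2g).

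The first part is the stratum-adjusted effect (pooled weights when the arms are of equal size). The second is imbalance.

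**Three illustrative data sets**, 50 per arm, with the same assumed stratum rates in both arms (about 50/20/25/10%, rounded to whole responders):

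| Stratum counts, Arm 1 vs Arm 2 | Responders | Crude | Own weights | Pooled weights | Pr(Arm 1 - Arm 2 > 0), own vs pooled | Pr(Arm 2 - Arm 1 > -0.05), own vs pooled |
|---|---|---|---|---|---|---|
| 16/18/4/12 vs 14/20/4/12 | 14 vs 13 | +2.0 | +2.0 | +0.8 | 0.59 vs 0.54 | 0.65 vs 0.70 |
| 18/16/4/12 vs 14/20/4/12 | 14 vs 13 | +2.0 | +2.0 | -0.4 | 0.59 vs 0.48 | 0.65 vs 0.75 |
| 20/15/4/11 vs 12/20/4/14 | 15 vs 12 | +6.0 | +6.0 | +0.5 | 0.77 vs 0.52 | 0.45 vs 0.71 |

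Own-weight and crude differences agree to four decimals at the maximum-likelihood fit, and MCMC means are within 0.1 point. In the second row the share differences are +0.08 and -0.08 in strata 1 and 2, where the fitted rates average 0.498 and 0.197. The imbalance part is 0.08 x (0.498 - 0.197) = 0.024, which is the gap between +2.0 and -0.4 points. The fitted arm coefficient there is -0.024 on the log-odds scale, so the planned difference has the opposite sign to the model's own arm effect. The third row is more unbalanced than stratified blocks would usually allow; it shows sensitivity, not expected size.

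**Expected size.** Stratum shares, stratum rates, block size and re-stratification rate are not in the documents. Assumed: shares 25/45/8/22%, rates 50/20/30/5%, blocks of 4, N = 100, no arm effect.

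| Analysed in another HBsAg stratum | SD of imbalance part | SD of difference, own weights | SD, pooled weights |
|---|---|---|---|
| 0% | 0.6 points | 7.86 | 7.87 |
| 5% | 1.4 points | 8.06 | 7.95 |
| 10% | 1.8 points | 8.40 | 8.28 |

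The imbalance part averages zero. Its 97.5th percentile (signed) is about 2.7 points at 5% and 3.5 points at 10%. The reduction in SD is nil, then (8.06 - 7.95)/8.06 = 1.4% and (8.40 - 8.28)/8.40 = 1.4%. With more prognostic strata it reaches about 5%.

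Across two assumed stratum mixes and three assumed rate patterns, the 95th percentile of the absolute shift is 0.9 to 2.0 points with correct stratification (blocks of 4 or 6) and 1.7 to 4.5 points with 5 to 10% re-stratification. As a yardstick, the simple standard error at 27% SVR is the square root of 2 x 0.27 x 0.73 / 50, or 8.9 points.

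**The case against.** The strongest reply is that nothing is wrong against the stated estimand. The target is a marginal difference in percentages, and under randomisation the crude difference estimates it without bias. Pooled standardisation estimates the same quantity with slightly less chance variation. That stands, and it defines the point: precision is forgone and no error is introduced.

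A reader might infer that the regimen comparison is biased, or that imbalance could by itself use up the 5-point margin. The documents do not support either. The shift has mean zero and, with correct stratification, an SD well under one point. The larger figures need a re-stratification rate that the documents do not give, and the rule in SAP section 4.1.1 is worded for incorrect assignments. Protocol section 4.1 does not say whether the screening or the Day 1 HBsAg value sets the stratum, so drift between the two is possible but not shown.

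A second tempting reading starts from the written-out stratum equations in SAP section 4.2.2, which omit gamma_3. Taken literally, stratum rates would be identical in both arms and the whole difference would come from the weights. The model equation just above them includes the arm term, so this is better read as a slip in notation.

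Two further replies stand. The SAP attaches no decision threshold to the two probabilities; the framework sits in the iDRC charter, which is not among the documents. And SAP section 4.6.1 reports SVR by HBsAg and HBeAg subgroup within arm, so a marked imbalance would be visible. The change also has a price: with different weights for the contrast, the reported difference will not exactly match the two reported arm rates.

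**Conclusion.** The mechanism holds: as specified, the Arm 1 minus Arm 2 point estimate is in effect unadjusted although the model carries the stratification factors. The algebra depends only on the arm term and the near-flat priors. Responses imputed for wide disruptive events would loosen the equality slightly.

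The consequence is minor. The SD of the imbalance part is about 0.6 points, or 1.4 to 1.8 points under the assumed 5 to 10% re-stratification, against a sampling SD of about 8 points. The expected gain in precision is roughly 0 to 1.5%, larger if the strata are more prognostic than assumed. In a particular trial with uneven strata, the two probabilities could still move by several hundredths, as the first two illustrative data sets show. The single-arm SVR rates, which are the primary estimand, are not affected. This is a cheap improvement and not a correction on which the study's conclusions depend.

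**What to change.** In SAP section 4.3.1.3 only, state that:

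- each arm's stratum rates include gamma_3 where the arm indicator applies;
- for each posterior draw, each arm's rate is the weighted average of its four stratum rates, using common weights equal to the stratum total over both arms divided by N;
- the difference and both posterior probabilities are taken from these draws.

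Own-arm weights stay for the single-arm SVR rates in section 4.2.2. Specifying the calculation draw by draw also settles, for the contrast, how the mixture wording in section 4.2.2 is to be implemented. The same edit should correct the written-out stratum equations and give gamma_3 a prior, since priors are listed only for k = 1, 2.

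The cost is a few lines of SAP text, a small program change, and a table footnote explaining why the adjusted difference need not equal the difference between the two reported arm rates. No extra data are needed.
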